5.2. Investigational Product Administration

Previously read:

Each SC injection will be administered by qualified and appropriately trained clinical staff to different quadrants in the abdomen. There are no posture requirements for dosing (see Table 1). mg dose group injection with a total volume of mL will be administered. In the mg dose groups injections and injections, respectively, of mL each will be administered. Where multiple injections are administered the injection site in different quadrants of the abdomen.

Now reads:

Each SC injection will be administered by qualified and appropriately trained clinical staff to different quadrants in the abdomen. There are no posture requirements for dosing (see Table 1). mg dose group, injection with a total volume of mL will be administered. In the mg dose groups, injections and injections, respectively, of mL each will be administered. Where multiple injections are administered, the injection sites will be located in different quadrants of the abdomen.

## LIST OF ABBREVIATIONS

Abbreviations pertain to the statistical analysis plan (SAP) only (not the tables, figures, and listings [TFLs]).

%AUC extrap	percentage of area under the plasma concentration-time curve due to extrapolation from the last quantifiable concentration to infinity
ADaM	Analysis Data Model
AE	adverse event
AUC	area under the concentration-time curve
AUC inf	area under the plasma concentration-time curve from time zero extrapolated to infinity
AUC last	area under the plasma concentration-time curve from time zero to the last quantifiable concentration
BLQ	below the limit of quantification
CDISC	Clinical Data Interchange Standards Consortium
CDER	Center for Drug Evaluation and Research
CL/F	apparent total clearance
C max	maximum observed plasma concentration
COVID-19	coronavirus disease 2019
CRU	clinical research unit
CSR	clinical study report
CTCAE	Common Terminology Criteria for Adverse Events
DMP	data management plan
ECG	electrocardiogram
EOS	end of study
eCRF	electronic case report form
ICF	informed consent form
ICH	International Council for/Conference on Harmonisation
λ z	apparent terminal elimination rate constant
λ z Lower	start of exponential fit
λ z N	number of data points included in the log-linear regression
λ z Span Ratio	time period over which λ z was determined as a ratio of t 1/2
λ z Upper	end of exponential fit
MedDRA	Medical Dictionary for Regulatory Activities
NA	not applicable
PK	pharmacokinetic(s)
R  -adj	adjusted coefficient for determination of exponential fit
SAP	statistical analysis plan
SC	subcutaneous

---

SD	standard deviation
SDV	source document verification
$t_{1/2}$	apparent terminal elimination half-life
TEAE	treatment-emergent adverse event
TFL	table, figure, and listing
$t_{last}$	time of the last quantifiable concentration
$t_{max}$	time of the maximum observed plasma concentration
$V_z/F$	apparent volume of distribution during the terminal phase
WHODrug	World Health Organization Drug Dictionary

## 1. INTRODUCTION

This SAP has been developed after review of the clinical study protocol (Amendment 1 dated 24 August 2021) and electronic case report form (eCRF).

This SAP describes the planned analysis of the pharmacokinetic (PK), safety, and tolerability data from this study. A detailed description of the planned TFLs to be presented in the clinical study report (CSR) is provided in the accompanying TFL shells document.

In general, the analyses are based on information from the protocol, unless they have been modified by agreement with Amgen Inc. A limited amount of information about this study (eg, objectives, study design) is given to help the reader's interpretation.

This SAP must be finalized prior to the lock of the clinical database. Additionally, the SAP and TFL shells should be finalized prior to any programming activities commencing.

This SAP supersedes any statistical considerations identified in the protocol; where considerations are substantially different, they will be so identified. If additional analyses are required to supplement the planned analyses described in this SAP, they may be performed and will be identified accordingly in the CSR. Any substantial deviations from this SAP will be agreed with Amgen Inc. and identified in the CSR.

This SAP is written with consideration of the recommendations outlined in the International Conference on Harmonisation (ICH) E3 guideline *Structure and Content of Clinical Study Reports*, ICH E8 guideline *General Considerations for Clinical Trials*, ICH E9 guideline *Statistical Principles for Clinical Trials*.

The document history is presented in [Appendix 1](#).

## 2. STUDY OBJECTIVES

The primary objective of the study is:

- to evaluate the PK of AMG 133 after single subcutaneous (SC) administration in healthy Japanese and Caucasian subjects.

The secondary objectives of the study are:

- to evaluate the safety and tolerability of AMG 133 after single SC administration in healthy Japanese and Caucasian subjects.
- to evaluate the incidence of anti-AMG 133 antibodies in healthy Japanese and Caucasian subjects.

## 3. STUDY ENDPOINTS

The primary endpoints of the study are AMG 133 PK parameters:

- maximum observed plasma concentration ( $C_{max}$ )

- area under the plasma concentration-time curve (AUC) from time zero to the last quantifiable concentration (AUClast)
- area under the plasma concentration-time curve from time zero extrapolated to infinity (AUCinf).

The secondary endpoints of the study are:

- adverse events (AE)
- clinical laboratory tests
- 12-lead electrocardiograms (ECGs)
- vital signs
- incidence of anti-AMG 133 antibodies.

#### 4. STUDY DESIGN

This will be a Phase I, single-center, open-label, randomized, parallel-arm study to investigate the PK, safety, and tolerability of a single SC dose of AMG 133 in 3 groups of healthy Japanese subjects and 2 groups of healthy Caucasian subjects.

Approximately 35 subjects will be enrolled in total, with 7 subjects in each of the 5 groups.

Potential subjects will be screened to assess their eligibility to enter the study within 28 days prior to dose administration. Eligible subjects will be admitted into the clinical research unit (CRU) for Check-in on Day -1 and be confined to the CRU until clinic discharge on Day 8. On Day 1, 21 Japanese subjects will be randomly assigned in a 1:1:1 ratio to Group 1, 2, or 3, and 14 Caucasian subjects will be randomly assigned in a 1:1 ratio to either Group 4 or 5. Each subject will participate in 1 treatment group only.

On Day 1, AMG 133 will be administered as a single SC dose to the following groups:

- Group 1: [REDACTED] mg (Japanese subjects)
- Group 2: [REDACTED] mg (Japanese subjects)
- Group 3: [REDACTED] mg (Japanese subjects)
- Group 4: [REDACTED] mg (Caucasian subjects)
- Group 5: [REDACTED] mg (Caucasian subjects)

[figure not shown]
The total duration of study participation for each subject (from Screening through end of study [EOS] visit) is anticipated to be approximately 21 weeks.

The start of the study is defined as the date the first enrolled subject signs an Informed Consent Form (ICF). The point of enrollment occurs at the time of subject number allocation.

The end of the study is defined as the date of the last subject's last assessment (scheduled or unscheduled).

An overview of the study design is shown in [Figure 1](#).

**Figure 1: Study Design**

## 5. SAMPLE SIZE JUSTIFICATION

The sample size for this study is based on practical considerations. No statistical hypotheses will be tested. Approximately 35 subjects will be enrolled across 5 groups (7 subjects per group). The study design and sample size per dose group for this study is considered adequate for evaluation of the study objectives.

## 6. STUDY TREATMENTS

The study treatment names, abbreviations, and ordering to be used in the TFLs are presented in [Table](#).

Table 1: Presentation of Study Treatments in TFLs

Treatments	Abbreviation	Order in TFLs
Group 1: [REDACTED] mg (Japanese subjects)	Japanese [REDACTED] mg AMG 133	1
Group 2: [REDACTED] mg (Japanese subjects)	Japanese [REDACTED] mg AMG 133	2
Group 3: [REDACTED] mg (Japanese subjects)	Japanese [REDACTED] mg AMG 133	3
Group 4: [REDACTED] mg (Caucasian subjects)	Caucasian [REDACTED] mg AMG 133	4
Group 5: [REDACTED] mg (Caucasian subjects)	Caucasian [REDACTED] mg AMG 133	5

All TFLs will be based on actual treatments (eg, if subject was assigned to receive Group 1 treatment but was wrongfully dosed with Group 3 treatment they would be summarized and listed under Group 3 treatment).

## 7. DEFINITIONS OF POPULATIONS

Any protocol deviations, including those due to coronavirus disease 2019 (COVID-19) and related restrictions (see [Section 8.1.1](#)), will be considered prior to database lock for their importance and taken into consideration when assigning subjects to populations.

### 7.1. All Subjects Population

The all subjects population will include all subjects who signed the ICF and had any study assessment recorded in the database per the protocol.

### 7.2. Safety Population

The safety population will include all subjects who received at least 1 dose of AMG 133.

### 7.3. Pharmacokinetic Population

The PK population will include all subjects who received at least 1 dose of AMG 133 and have evaluable PK data.

## 8. STATISTICAL METHODOLOGY

### 8.1. General

Listings will be provided for all data captured in the database, with the exception of medical history. Listings will include all subjects assigned to the all subjects population and include data up to the point of study completion or discontinuation. Subjects are generally considered to have completed the study if they complete the scheduled end of study visit (rather than early termination visit). Any subject who discontinues the study will be identified accordingly in the listings. Summaries and statistical analyses will include the subjects assigned to the relevant population based on data type.

Data analysis will be performed using the SAS® statistical software package Version 9.4 (or higher if a new version is issued during the study).

Analysis Data Model (ADaM) datasets will be prepared using Clinical Data Interchange Standards Consortium (CDISC) ADaM Version 2.1 (or higher if a new version is issued during the study) and CDISC ADaM Implementation Guide Version 1.2 (or higher if a new version is issued during the study). Pinnacle 21 Enterprise Version 4.2.0 (or higher if a new version is issued during the study) will be utilized to ensure compliance with CDISC standards.

Caution should be used when interpreting results from the statistical analyses conducted in this study because the sample size is not based on power calculations.

Where reference is made to 'valid' data, this refers to non-missing data which meet the predetermined criteria (eg, are not flagged for exclusion).

Where reference is made to 'all calculations', this includes, but is not limited to, summary statistics, statistical analyses, baseline derivation, changes from baseline, percentage changes from baseline, and any parameter derivations.

All figures will be produced on linear-linear or discrete-linear scales, as applicable, unless specifically stated otherwise.

### **8.1.1. Handling of Data Quality Issues Due to Coronavirus Disease 2019 and Related Restrictions**

Due to COVID-19 and related restrictions, there is a high risk for impact to data integrity, with the recognized potential for:

- Missed visits, caused by, for example:
  - Subject unable to travel to site due to restrictions, the need to quarantine, or COVID-19 infection
  - Subject unwilling to go to site due to fear of COVID-19 infection
  - Site postponing subject's visit due to investigator not being available (eg, if they have been dispatched to hospital handling COVID19 infections)
- Site unable to replenish supply of investigational product
- Incomplete data entry by sites due to limited resources to support study or no access to source documents or to eCRF
- Outstanding source document verification (SDV) due to sponsor or country restrictions on remote SDV, or no or limited access to site(s) for on-site visits
- Unanswered queries

At the time of the reporting of the study results, all protocol deviations due to COVID-19 or related restriction will be assessed for their severity and impact on the analyses. If needed, appropriate statistical methods will be applied as a mitigating action (eg, data might be categorized into 2 analysis groups, with and without COVID-19 and related restrictions impact); however, this will exclude any imputations of the missing values. Any mitigating actions will be agreed with Amgen Inc. in advance and identified in the CSR.

### **8.1.2. Calculation of the Summary Statistics**

For continuous data the following rules will be applied:

- Missing values will not be imputed, unless specifically stated otherwise.
- Unrounded data will be used in the calculation of summary statistics.

- If the number of subjects with valid observations (n) <3, summary statistics will not be calculated, with the exception of n, minimum, and maximum.
- In general, as early termination data are not associated with any scheduled timepoint, they will be excluded from all calculations of summary statistics and statistical analyses. Exceptions may be made where justified.

For categorical data the following rules will be applied:

- For ordered categorical data (eg, AE severity), all categories between the possible minimum and maximum categories will be included, even if n = 0 for a given category.
- For non-ordered categorical data (eg, race), only those categories for which there is at least 1 subject represented will be included; unless specifically stated otherwise.
- Missing values will not be imputed, unless specifically stated otherwise. A ‘missing’ category will be included for any parameter for which information is missing. This will ensure that the population size totals are consistent across different parameters.

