2. OBJECTIVES AND ENDPOINTS

2.1. Objectives

The primary objective of the study is:

• to evaluate the PK of AMG 133 after single SC administration in healthy Japanese and Caucasian subjects.

The secondary objectives of the study are:

- to evaluate the safety and tolerability of AMG 133 after single SC administration in healthy Japanese and Caucasian subjects.
- to evaluate the incidence of anti-AMG 133 antibodies in healthy Japanese and Caucasian subjects.

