4.5. Subject Withdrawal and Replacement

A subject is free to withdraw from the study at any time. In addition, a subject will be withdrawn from dosing if any of the following criteria are met:

- change in compliance with any inclusion/exclusion criterion that is clinically relevant and affects subject safety as determined by the Investigator (or designee)
- noncompliance with the study restrictions that might affect subject safety or study assessments/objectives, as considered applicable by the Investigator (or designee)
- any clinically relevant sign or symptom that, in the opinion of the Investigator (or designee), warrants subject withdrawal.

If a subject is withdrawn from dosing, the Sponsor (or designee) will be notified and the date and reason(s) for the withdrawal will be documented in the subject's electronic Case Report Form (eCRF). If a subject is withdrawn, efforts will be made to perform all EOS assessments, if possible (Appendix 8). Other procedures may be performed at the Investigator's (or designee's) and/or Sponsor's discretion. If the subject is in-house, these procedures should be performed before the subject is discharged from the clinic. The Investigator (or designee) may also request that the subject return for an additional follow-up visit. All withdrawn subjects will be followed until resolution of all their adverse events, serious adverse events, or until the unresolved adverse events, serious adverse events are judged by the Investigator (or designee) to have stabilized.

Protocol Reference: 20200290

Subjects who are withdrawn for reasons not related to study drug may be replaced following discussion between the Investigator and the Sponsor. Subjects withdrawn as a result of adverse events/serious adverse events thought to be related to the study drug will generally not be replaced.

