#### **8.6.4. 12-lead Electrocardiogram Parameters**

All 12-lead ECG parameters will be listed; any value outside the clinical reference range will be flagged.

Summary tables by treatment and timepoint will be provided for all 12-lead ECG parameters.

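### By default the post-dose ECG summary covers completers only, because SAP 8.1.2 leaves out early-termination values and the only scheduled post-dose ECG is at EOS/ET

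*SAP*

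**What the plan says.** A secondary objective (Protocol 2.1) is "to evaluate the safety and tolerability of AMG 133 after single SC administration in healthy Japanese and Caucasian subjects". ECGs, vital signs and laboratory tests are secondary endpoints in both documents, and the safety population is everyone who received AMG 133 (SAP 7.2).

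On early termination, Protocol 4.5 says: "If a subject is withdrawn, efforts will be made to perform all EOS assessments, if possible". On replacement, the same section says: "Subjects withdrawn as a result of adverse events/serious adverse events thought to be related to the study drug will generally not be replaced".

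SAP 8.1.2, in its rules for continuous data, says that "as early termination data are not associated with any scheduled timepoint, they will be excluded from all calculations of summary statistics and statistical analyses". The sentence opens with a general qualifier and is followed by "Exceptions may be made where justified". No criteria are given for those exceptions.

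For ECGs, SAP 8.6.4 plans: "Summary tables by treatment and timepoint will be provided for all 12-lead ECG parameters". SAP 8.1.4 keeps unscheduled values out of every calculation. SAP 8.1 generally counts a subject as having completed the study if the scheduled EOS visit, rather than an ET visit, took place.

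**The concern.** The reason given for the exclusion is that ET data have no scheduled timepoint. That is a good reason not to place an ET value in the Day 120 row. It is not a reason to leave the value out of every summary, and the protocol itself puts EOS and ET in one column of the schedule.

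For most endpoints the practical loss is limited, because a subject who leaves has already supplied scheduled post-dose values. ECG is different. If the only scheduled post-dose ECG is the one at EOS/ET, the default rule removes an early-terminated subject from the post-dose ECG summary altogether, even when the ET recording was made. A table meant to describe all dosed subjects then describes those who reached Day 120. Because the exceptions have no criteria, whether to include an ET value would be settled case by case, with values visible, in an open-label study.

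**Working it through.** **Step 1. Check the reading of the schedule.** The Appendix 8 table was read from PDF, so the column positions were tested against the blood-volume table in Protocol Appendix 3. The visits read from the schedule give 8 laboratory, 16 PK and 5 antibody samples. With the stated volumes:

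8 × 7.5 + 3.5 + 4 + 4 + 16 × 4 + 5 × 4 = 155.5 mL.

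This equals the Appendix 3 total. The planned size also reproduces: 5 groups × 7 = 35.

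**Step 2. Count scheduled post-dose assessments.** The Day 1 column is headed predose, so Day 1 values are counted as baseline.

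| Assessment | Post-dose days | Total | Before EOS |
|---|---|---|---|
| ECG | 120 (EOS/ET) | 1 | 0 |
| Vital signs | 2, 3, 8, 15, 22, 29, 43, 57, 71, 92, 120 | 11 | 10 |
| Laboratory | 3, 8, 29, 57, 92, 120 | 6 | 5 |

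**Step 3. Apply SAP 8.1.2 and 8.1.4 to an early termination.** The entries are scheduled post-dose visits that remain in the summaries.

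| Leaves at about | ECG | Vital signs | Laboratory |
|---|---|---|---|
| Day 10 | 0 | 3 | 2 |
| Day 30 | 0 | 6 | 3 |
| Day 60 | 0 | 8 | 4 |

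The ECG entry is zero whenever the subject leaves. Additional ECGs are allowed by Protocol 7.3.4, but in the SAP's terms they are unscheduled and also excluded. For vital signs and laboratory tests the loss is the ET value alone.

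**Step 4. Size per event.** One ET subject leaves 6 of 7 in the post-dose ECG row (1/7 = 14.3% lost). Two leave 5 of 7 (28.6%). SAP 8.1.2 also says: "If the number of subjects with valid observations (n) <3, summary statistics will not be calculated, with the exception of n, minimum, and maximum". A group of 7 would reach that limit only with five early terminations.

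If one ET value differs by d from six otherwise equal values, leaving it out changes the group mean by d/7. Assumed differences of 30 and 60 ms give 30/7 = 4.3 ms and 60/7 = 8.6 ms. If the value is the highest in its group, the maximum changes by d. These are illustrations, since the plan gives no expected ECG values.

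**Step 5. How often it could arise.** No dropout rate is stated. With an assumed rate p, the chance of at least one early termination among n subjects is 1 − (1 − p)^n.

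| Assumed p | Group of 7 | All 35 |
|---|---|---|
| 3% | 19% | 66% |
| 5% | 30% | 83% |
| 10% | 52% | 97% |
| 15% | 68% | over 99% |

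**Step 6. Exposure at the two kinds of visit.** Assume first-order decline from 168 h and, for want of a human figure, the monkey half-lives in Protocol 1.2 (189 to 284 h). The level relative to 168 h is then 2^(−(t − 168)/t½). At 504 h (Day 22) it is 29.2% to 44.0%. At 2856 h (Day 120) it is 0.005% to 0.142%. An ET ECG near Day 22 would therefore be taken at a level some 310 to 5,600 times that at Day 120: 2^(2352/284) to 2^(2352/189), where 2352 = 2856 − 504. The excluded ECG may be the more informative one about exposure. The same figures show why EOS and ET values should not be averaged together.

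**The case against.** The strongest reply is that the SAP does what a by-timepoint table requires. Every laboratory, vital-sign and ECG summary is by treatment and timepoint, and an ET value does not belong in a Day 120 row. The documents describe no overall minimum or maximum row from which ET values are being removed, so the fix asks for something new. All captured data except medical history are listed, discontinued subjects are identified, and out-of-range values are flagged. With about 35 subjects, a reader can find each ET value. The investigator assesses every ECG, and an abnormality judged clinically significant is an adverse event. Nothing here is inferential.

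Most of this stands, and it is why the point is minor. It does not remove the ECG gap. Listings do not change the n or the range in the table, and an early-terminated subject has no other route into the post-dose ECG summary.

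A reader might go further in three ways that the documents do not support.

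- **That the tolerability tables as a whole describe those who stayed.** The TEAE tables are counts, include events leading to discontinuation, and are outside the continuous-data rule. Scheduled laboratory and vital-sign values from before termination stay in their rows.
- **That the rule mainly removes subjects who stopped for tolerability.** Protocol 4.5 does list "any clinically relevant sign or symptom that, in the opinion of the Investigator (or designee), warrants subject withdrawal", but as a criterion for withdrawal from dosing, and this is a single-dose study. Drug-related withdrawals are foreseen and generally not replaced, so the loss could be related to outcome. However, SAP 8.1.1 also names travel limits, quarantine and fear of infection as reasons for missed visits.
- **That the bias runs towards better tolerability.** No rate or leading cause of termination is given, so the direction is not known.

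**Conclusion.** The point holds in a narrow form. Under the default rule, any subject who terminates early contributes no post-dose value to the ECG summary, so its post-dose row covers completers only while the stated population is all dosed subjects. For vital signs and laboratory tests, only the ET value is missing. The values are lost from summaries, not from the record.

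The size is one subject in seven (14.3%) of a group per early termination. Whether that shifts any result, and in which direction, cannot be said from the plan. The conclusion rests on reading the Day 1 ECG as predose and on the default being applied. The exception clause could restore an ET value, but without criteria it cannot be relied on. Severity: minor.

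**What to change.** In SAP 8.1.2, limit the exclusion of ET safety data to scheduled-timepoint rows, including the Day 120 EOS row. For safety data, replace the open-ended exception with a fixed rule: one row per treatment in the ECG table, *Last post-dose value (EOS or ET)*, based on the safety population. It would give n, the number of those n that are ET values, median, minimum and maximum. For consistency, add the same row to the laboratory and vital-signs tables. Leave the by-timepoint rows and SAP 8.1.4 unchanged. A subject with neither an EOS nor an ET value is not in the row, and the shortfall in n shows this.

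The cost is a short edit to SAP 8.1.2 and one row in up to three table shells, with no new visits or data. The shells are a separate document and were not available, so the programming effort is an estimate. The downside is that the row mixes different post-dose times and exposures. It should be read descriptively with the ET count in view, and it should not report a pooled mean.
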